		
specific language on the criteria.
 
4. Added language to Discontinuation of Study Intervention involving thromboembolic events see Section 7.1.
 
Rationale: to provide consistency across the program.
 
5. Added language to Safety Adjudication Committee Section 9.5.2.
 
Rational: to align with program language to specifically include events requiring adjudication are cardiovascular events including venous thromboembolic events (VTE).
 
6. The content of five Protocol Administrative Clarification Letters (PACLs) # 1-5 was added.
 
• PACL 1: 1) HIV serology should also include Hep B tests as described in EC #21. 2) Appendix 2 should include the above. 3) PROs should be completed in a certain same order (pre and post Day 15). 
Rationale: to ensure consistency throughout protocol.
 
• PACL 2: typographical error of absolute lymph count (should be 1000 not 800). 
Rationale: clarification.
 
• PACL 3 JAPAN Only: EC #23 clarified subjects will have HBV DNA testing if there is no documentation of HBV vaccination. 
Rationale: country requirement.
 
• PACL 4: Concomitant medications guselkumab and risankizumab were added to the agents requiring 6-month
--	--	----------------------------------------------------------------------------------------------------------------------------------------------------------------------------------------------------------------------------------------------------------------------------------------------------------------------------------------------------------------------------------------------------------------------------------------------------------------------------------------------------------------------------------------------------------------------------------------------------------------------------------------------------------------------------------------------------------------------------------------------------------------------------------------------------------------------------------------------------------------------------------------------------------------------------------------------------------------------------------------------------------------------------------------------------------------------------------------------------------------------------------------------------------------------------------------------------------------------------------------------------------------------------------------------------------------------------------------------------------------------------------------------------------------------------------------------------

		
washout.
 
Rationale: frequently asked question by Investigators regarding new therapeutics.
 
• PACL 5: 1) C-SSRS footnote to clarify the use of “Lifetime” version at baseline. 2) PRO footnote to clarify pre-dose to be consistent with other sections. 3) discrepancy clarified that no live vaccines allowed 8 weeks after last dose. 4) Justification for Dose section 4.3 discrepancy corrected to confirm 83% not 82%. 
Rationale: to ensure consistency throughout protocol.
 
• Additional discrepancies were eliminated, and typographical errors corrected.
Original protocol	14 December 2018	N/A

This amendment incorporates all revisions to date, including amendments made at the request of country health authorities and institutional review boards (IRBs)/ethics committees (ECs).

TABLE OF CONTENTS

LIST OF TABLES	10
1. PROTOCOL SUMMARY	11
1.1. Synopsis	11
1.2. Schema	16
1.3. Schedule of Activities (SoA).....	17
2. INTRODUCTION	21
2.1. Study Rationale	21
2.2. Background	21

1. PROTOCOL SUMMARY

1.1. Synopsis

Rationale: This multicenter study is being conducted to provide additional PF-06826647 safety and tolerability data, and to further explore the clinical efficacy of PF-06826647 in the treatment of moderate to severe plaque psoriasis. Additionally, the study is intended to enable selection of oral dose and dosing regimen for the future clinical development of PF-06826647.

Objectives, Endpoints, and Estimands:

Investigational Treatment Period:

Objectives	Endpoints	Estimands
Primary:	Primary:	Primary:

To compare the efficacy of multiple dose levels of PF-06826647 versus placebo on the proportion of participants with moderate to severe plaque psoriasis achieving PASI 90.
	
 Proportion of participants achieving PASI 90 (90% or greater improvement from Baseline) at Week 16. 	
Estimand E1: This estimand is intended to provide a population level estimate of the treatment effect of the IP alone on a binary responder endpoint; without the benefit of additional prohibited medications, regardless of participants compliance with the IP dosing.
 
Population: Participants with moderate to severe plaque psoriasis as defined by the inclusion and exclusion criteria without the benefit of additional prohibited medication regardless of compliance.
 
Intercurrent Events: A) Prohibited medication –response will be considered negative for participants after receiving prohibited medication. B) Withdrawal and all other events leading to missing data will be treated as in A. C) Inadequate compliance – participants data will be used as recorded.
 
Population level summary: The difference in proportions between treated and placebo response rates.

Secondary:	Secondary:	Secondary:
To compare the efficacy of multiple dose levels of PF-06826647 versus placebo on the proportion of participants with moderate to severe plaque psoriasis achieving PASI 75.	Key secondary endpoint: 
 Proportion of participants achieving PASI 75 (75% or greater improvement from Baseline) at time points specified in the Schedule of Activities (SoA). 	The binary secondary endpoints, when appropriate, will be analyzed descriptively and using estimand E1.
To compare the efficacy of multiple dose levels of PF-06826647 versus placebo on PGA score in participants with moderate to severe plaque psoriasis.	
 Proportion of participants with PGA score clear (0) or almost clear (1) and ≥ 2 points improvement from baseline at time points specified in the SoA. Proportion of participants with PGA score clear (0) or almost clear (1) at time points specified in the SoA. 	
To compare the efficacy of multiple dose levels of PF-06826647 versus placebo on the proportion of participants with moderate to severe plaque psoriasis achieving PASI 50 and PASI 100.	
 Proportion of participants achieving PASI 50 (50% or greater improvement from Baseline), PASI 100 (100% from Baseline) at time points specified in the SoA. 	
To compare the efficacy of multiple dose levels of PF-06826647 versus placebo on PGA and PASI scores in participants with moderate to severe plaque psoriasis.	
 Change from baseline and percent change from baseline in PASI scores at time points specified in the SoA. 	Estimand E2: This estimand is intended to provide a population level estimate of the treatment effect of the IP alone on a continuous endpoint; without the benefit of additional prohibited medications, regardless of participants compliance with the IP dosing.
To compare the effect of multiple dose levels of PF-06822647 versus placebo in Peak-Pruritus Numerical Rating Scale score in participants with moderate to severe plaque psoriasis.	
 Absolute score and change from baseline in Peak-Pruritus Numerical Rating Scale score at time points specified in the SoA. 	Population: Participants with moderate to severe plaque psoriasis as defined by the inclusion and exclusion criteria without the benefit of additional prohibited medications regardless of compliance. Intercurrent Events: A) Prohibited medication – all scores after participants receive prohibited

		
medication will be omitted from the analysis and treated as missing scores. Missing scores will be imputed based on the assumption that participants do not benefit from the IP treatment.
 
B) Withdrawal and all other events leading to missing data will be treated similarly as in A.
 
C) Inadequate compliance – participants data will be used as recorded.
 
Population level summary:
 
The mean difference between treated and placebo arms of the change from baseline PASI score.
 
All continuous endpoint, when appropriate will be analyzed descriptively and using estimand E2 described above when appropriate.

To assess the safety and tolerability of PF-06826647 in participants with moderate to severe plaque psoriasis.
	
 • Incidence and severity of adverse events, serious adverse events and withdrawals due to adverse events. • Change from baseline in clinical laboratory values (chemistry and hematology, lipids). • Incidence of clinically significant changes in ECG (heart rate, QT, QTc, PR and QRS intervals). • Change from baseline in vital signs (blood pressure, pulse rate and temperature measurements). 	
There is no defined estimand for these endpoints and they will be analyzed using Pfizer data standards as applicable.

To compare the efficacy of multiple dose levels PF-06826647 versus placebo on measures of disease and symptom severity in participants with moderate to severe plaque psoriasis.
	
 • Absolute score and change from baseline Psoriasis Symptom Inventory at time points specified in the SoA. 	
These endpoints will be analyzed descriptively and using estimand E2 described above when appropriate.

Extension Treatment Period:

Objectives	Endpoints	Estimands
Primary:	Primary:	Primary:
To assess the safety and tolerability of PF-06826647 in participants with moderate to severe plaque psoriasis.	
 • Incidence and severity of adverse events, serious adverse events and withdrawals due to adverse events. • Change from baseline in clinical laboratory values (chemistry, hematology & lipids). • Incidence of clinically significant changes in ECG (heart rate, QT, QTc, PR and QRS intervals). • Change from baseline in vital signs (blood pressure, pulse rate and temperature measurements). 	Not Applicable-will be analyzed descriptively and according to the Pfizer standard.

Overall Design:

This is a Phase 2b, randomized, double blind, placebo controlled, and multicenter study in participants with moderate to severe plaque psoriasis. Following a Screening period of up to 6 weeks, is a 16 week placebo controlled Investigational Treatment Period with double blind oral daily treatment using the following doses: 50 mg, 100 mg, 200 mg, 400 mg. All participants completing the 16 week Investigational Period may continue on to a 24 week non-placebo controlled Extension Treatment Period with double blind oral daily treatment, if per the Investigator judgment the participant is compliant with study procedures and continued participation presents no safety risks. The participants continuing into the Extension Treatment Period that were originally randomized to the 200 mg and 400 mg treatment groups will continue on their respective doses, while those randomized to one of the other treatment groups (including placebo) will be randomly assigned (at study baseline) to receive either 200 mg or 400 mg during the Extension Treatment Period. The total duration of study participation will be approximately 50 weeks, including up to 6 weeks Screening, 16 week Investigational Treatment Period, 24 week Extension Treatment Period and a Follow-Up visit 4 weeks after the Extension Period ends.

Number of Participants:

Approximately 160 participants (40 participants in each of the following arms: placebo, 200 mg, and 400 mg; and 20 participants in each of the following arms: 50 mg and 100 mg) will be randomly assigned to a treatment group in order to ensure a minimum of 128 evaluable participants completing Week 16 (assuming a 20% dropout rate).

Intervention Groups and Duration:

During the Investigational Treatment Period (Weeks 0 through 16), the 160 participants will receive PF-06826647 (50 mg, 100 mg, 200 mg, 400 mg) once daily, or matching placebo and the same participants will continue onto the Extension Treatment Period.

After completion of the 16 week placebo controlled Investigational Study Period, participants may transition directly into the 24 week Extension Study Period.

The total duration of study participation will be approximately 50 weeks, including up to 6 weeks Screening, 16 week Investigational Treatment Period, the 24 week Extension Treatment Period and a Follow-Up visit 4 weeks after the Extension Period ends.

Data Monitoring Committee:

This study will use an internal review committee (IRC) ([Section 9.5.1](#)).

[figure not shown]
Statistical Methods:

The primary estimand will be the population average treatment effect on PASI 90 rates at Week 16 relative to placebo without regard to compliance in the absence of prohibited medication.

The analysis of the primary estimand will be of the proportion of participants achieving: PASI 75 (75% or greater improvement from Baseline); PGA score clear (0) or almost clear (1) and ≥ 2 points improvement from baseline; PGA score clear (0) or almost clear (1); PASI 50 (50% or greater improvement from Baseline) and PASI 100 (100% or greater improvement from Baseline). The analysis of the secondary estimand will be of the change from baseline and percent change from baseline in PASI scores; and absolute score and change from baseline in Peak-Pruritus Numerical Rating Scale score.

All other key secondary continuous clinical endpoints will be analyzed using the secondary estimand, while all other key secondary categorical clinical endpoints will be analyzed using the primary estimand.

1.2. Schema

1.3. Schedule of Activities (SoA)

The SoA table provides an overview of the protocol visits and procedures. Refer to the [STUDY ASSESSMENTS AND PROCEDURES](#) section of the protocol for detailed information on each procedure and assessment required for compliance with the protocol.

The investigator may schedule visits (unplanned visits) in addition to those listed in the SoA table, in order to conduct evaluations or assessments required to protect the well-being of the participant

Study Procedure	Screening	Baseline	Investigational Treatment Period							Extension Treatment Period		Follow-Up ^b	Early Termination ^c
			1	2	4	6	8	12	16	18/20/24/28/32/36	40		
Visit Identifier (Week)	-6 to -1	0	1	2	4	6	8	12	16	18/20/24/28/32/36	40	20 or 44	
Study Day ^a	-42 to -1	1	8	15	29	43	57	85	113	127/141/169/197/225/253	281	141 or 309	
Visit Window (Days)	N/A		±1	±1	±2	±2	±2	±2	±2	±3	±3	±3	
Enrollment Procedures													
Informed consent	X												
Medical history & demography	X												
Eligibility assessment	X	X											
Medication History	X												
Randomization		X											
Clinical Assessments													
Full Physical Exam	X	X							X		X		X
Brief Physical Exam			X	X	X	X	X	X		X		X	
Vital signs ^d	X	X	X	X	X	X	X	X	X	X	X	X	X
ECG ^d	X	X			X				X		X		X
Height/Weight ^e	X	X							X		X		
Chest radiograph ^f	X												
C-SSRS ^g	X	X							X		X		
Laboratory Assessments													
Hematology/Blood chemistry	X	X	X	X	X	X	X	X	X	X	X	X	X
Lipid panel ^h (fasting)		X			X				X		X		
Urinalysis ⁱ	X	X			X				X		X		
FSH ^j	X												
Serum β-HCG ^k	X												

Study Procedure	Screening	Baseline	Investigational Treatment Period							Extension Treatment Period		Follow-Up ^b	Early Termination ^c
			1	2	4	6	8	12	16	18/20/24/28/32/36	40		
Visit Identifier (Week)	-6 to -1	0	1	2	4	6	8	12	16	18/20/24/28/32/36	40	20 or 44	
Study Day ^a	-42 to -1	1	8	15	29	43	57	85	113	127/141/169/197/225/253	281	141 or 309	
Visit Window (Days)	N/A		±1	±1	±2	±2	±2	±2	±2	±3	±3	±3	
Urine β-HCG ^l (done at site)		X	X	X	X	X	X	X	X	X	X	X	X
HIV serology/HBsAg, HBcAb, (HepB reflex testing), and HCVAb ^m	X												
Tuberculosis test ⁿ	X												
CCI [REDACTED]													
CCI [REDACTED]													
Study treatment													
IP dispensing ^q		X	X	X	X	X	X	X	X	X	X		
IP accountability			X	X	X	X	X	X	X	X	X	X	X
Dosing diary ^r			X	X	X	X	X	X	X	X	X	X	X
Clinical Assessments of psoriasis													
PASI, CCI PGA	X	X	X	X	X	X	X	X	X	X	X	X	X
PROs ^s													
Psoriasis Symptom Inventory		X	X	X	X		X	X	X	X ^t	X	X	X
PP-NRS		X	X	X	X		X	X	X	X ^t	X	X	X
[REDACTED]													
[REDACTED]													

Study Procedure	Screening	Baseline	Investigational Treatment Period							Extension Treatment Period		Follow-Up ^b	Early Termination ^c
			1	2	4	6	8	12	16	18/20/24/28/32/36	40		
Visit Identifier (Week)	-6 to -1	0	1	2	4	6	8	12	16	18/20/24/28/32/36	40	20 or 44	
Study Day ^a	-42 to -1	1	8	15	29	43	57	85	113	127/141/169/197/225/253	281	141 or 309	
Visit Window (Days)	N/A		±1	±1	±2	±2	±2	±2	±2	±3	±3	±3	
										CCI			
Monitoring													
Contraception Check ^v		X	X	X	X	X	X	X	X	X	X	X	X
Concomitant Treatment(s)		X	X	X	X	X	X	X	X	X	X	X	X
AE monitoring	X	X	X	X	X	X	X	X	X	X	X	X	X

Abbreviations: AE= adverse event; CCI  C-SSRS= Columbia Suicide Severity Rating Scale; CCI 
 CCI  ECG = electrocardiogram; CCI  FSH= follicle stimulating hormone; HBsAg= hepatitis B surface antigen; HBcAb= hepatitis B core antibody; HCVAb= hepatitis C virus antibody; β-HCG= human chorionic gonadotropin; HIV= human immunodeficiency virus; IP = Investigational Product; PASI = Psoriasis Area and Severity Index; PP-NRS= Peak-Pruritus Numerical Rating Scale PE= physical exam; PGA= Physician’s Global Assessment; PRO = patient reported outcome; WOCBP= women of child-bearing potential.

- Days relative to Day 1.
- Perform Follow-Up visit to the Investigational Treatment Period at Week 20 only if the participant does not continue into the Extension Treatment Period. Otherwise Follow-Up is completed at Week 44.
- Participants who prematurely withdraw during Investigational Treatment Period or during the Extension Treatment Period should return for an Early Termination (ET) visit occurring 1 week after their last dose whenever possible and continue visits per Investigator’s discretion until the event has returned to normal or baseline levels or is deemed clinically stable.
- 12-lead locally read singlicate ECG should be performed after the participant has rested quietly for at least 10 minutes and before laboratory blood collection. Vital signs consist of blood pressure, pulse rate, and temperature and should be performed before laboratory blood collection and after 5 minutes rest while preferably sitting (supine is allowed). Participants should not smoke or ingest caffeine 30 minutes prior to blood pressure and pulse rate measurements.
- Height only measured at Screening; height and weight will be measured without shoes.
- Chest X-ray or other appropriate chest diagnostic imaging (ie, CT or MRI) may be performed within 12 weeks prior to Day 1.
- Use C-SSRS “Lifetime” version at Screening and Baseline and “Since Last Visit” version at visits indicated in SoA. Participants who have recent or active suicidal ideation or behaviors will be excluded from study entry or after Day 1, would be discontinued from treatment and referred to a mental health professional for appropriate evaluation and treatment.
- Participants must be fasting (water only) for at least 8 hours prior to visits, when lipid panel is being assessed.
- Dipstick in all cases; microscopy analysis is indicated if urinalysis is positive for blood, nitrite, leukocyte esterase and/or protein. Urine culture is performed if urinalysis is positive for nitrite and/or leukocyte esterase or if clinically indicated.

- j. To be done in females (<60 years of age) who are amenorrheic for at least 12 consecutive months.
- k. Required for WOCBP at Screening
- l. Required for WOCBP prior to dosing at baseline and at all subsequent visits. To be conducted at the site. Pregnancy tests (serum or urine) may also be repeated more frequently as per request of IRBs/ECs or if required by local regulations.
- m. HepB reflex testing only if HBsAg negative but HBcAb positive at Screening. If result of HCVAb is positive, or if Hepatitis C Virus (HCV) antibody result is indeterminate, then a HCV RNA AMPLIPREP TAQMAN 2.0 will automatically be performed. In Japan see [Section 5.1](#) for HBV and HCV details.
- n. If not performed within 12 weeks prior to Screening (see Assessments [Section 8.2.1.1](#) for details).
- o. PK samples will be collected per [SoA](#) prior to dosing, and at 0.5 hour (± 5 min); at 1 and 2 hours (± 10 min) and 4 hours (± 20 min) post dose hours.
- C** [REDACTED]
- q. Participants should take blinded study medication daily during the Investigational Treatment Period and Extension Period; however, on study visit days, participants are instructed to refrain from dosing at home, and are to take the dose in the clinic.
- r. Participants will be reminded to complete the dosing diary daily throughout the study.
- s. All procedures should be performed before dosing of IP. Effort should be made to complete all PRO questionnaires before any other assessments except at Baseline when eligibility needs to be confirmed.
- t. Psoriasis Symptom Inventory, Peak-Pruritus Numerical Rating Scale **CCI** [REDACTED] scales to be completed daily for the first two weeks pre -dose as per [SoA](#) and at visits Weeks 4, 8, 12, 16, 24, 36 and Follow-up.
- C** [REDACTED]
- C** [REDACTED]
- v. To confirm that contraception, if assigned, is used consistently and correctly.

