6.1.1. Administration

Participants will swallow the investigational product (IP) whole and will not manipulate or chew the IP prior to swallowing. Participants will administer IP as outpatients, except on study visit days. On study visit days, participants should not take their dose of study drug until instructed to do so by the investigator or designated study site staff while at the study site.

Blinded PF-06826647 tablets and matching placebo for oral administration will be dispensed in blisters. Participants will be provided dosing instructions.

Sites will be trained on how participants should take tablets at home through an Investigational Product manual and/or other vehicle(s). Sites are responsible for communicating this information to participants; and site staff should review the dosing instructions with participants at every study visit.

Participants should take the IP orally once daily during the Investigational Treatment Period and the Extension Treatment Period of the study.

A temporary hold on dosing of the investigational product during the study for an individual participant for up to a maximum of 7 consecutive days is allowed once from Day 1 to Day 113, if the principal investigator (PI) deems it necessary because of infections (eg, upper respiratory infection, urinary tract infection), gastrointestinal (GI) disorders (eg, diarrhea, nausea, vomiting) or hematological abnormalities. Any temporary hold on dosing of the investigational product during the study should be recorded in the case report form (CRF).

It is recommended that the tablets be swallowed whole with ambient temperature water to a total volume of approximately 240 mL, and not to manipulate or chew the medication prior to swallowing; and **it is recommended to be taken with food**. On study visit days, participants are to be instructed to refrain from dosing at home and are to take the dose in the clinic from their current blister card and the dose from the newly dispensed blister card will be taken on the next day at home.

If a dose is missed and the interval to the next dose is less than 8 hours, the missed dose should not be administered.

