7. DISCONTINUATION OF STUDY INTERVENTION AND PARTICIPANT DISCONTINUATION/WITHDRAWAL

7.1. Discontinuation of Study Intervention

In rare instances, it may be necessary for a participant to permanently discontinue the investigational product. Per the study estimands, if investigational product is permanently discontinued, the participant will proceed to Early Termination per [Schedule of Activities](#). The site will inform sponsor medical monitor or sponsor clinician if the below criteria for permanent discontinuation of the IP are triggered.

Any participant meeting discontinuation criteria must have an Early Termination visit with their first visit occurring 1 week after their last dose whenever possible and continue visits per Investigator's discretion until the event has returned to normal or baseline levels or is deemed clinically stable.

The only exception to this is when a participant specifically withdraws consent for any further contact with him or her or persons previously authorized by the participant to provide this information.

Note that discontinuation of the investigational product does not represent withdrawal from the study.

Participants experiencing a thrombotic event as part of a serious adverse event must be discontinued from further IP administration and referred to a specialist for further evaluation of possible hypercoagulable state, as per local guidelines.

ECG Changes

A participant who meets either bulleted criterion below based on the average of triplicate ECG readings will be withdrawn from the IP administration.

- QTcF >500 msec;
- Change from baseline: QTc >60 msec.

If a clinically significant finding is identified (including, but not limited to, changes from baseline in QTcF after enrollment), the investigator or qualified designee will determine if the participant can continue in the study and if any change in participant management is needed. This review of the ECG printed at the time of collection must be documented. Any new clinically relevant finding should be reported as an AE.

Laboratory Abnormalities

All the following laboratory abnormalities require discontinuation if they are confirmed.
Confirmation through re-testing should occur within 48 hours:

Laboratory Variable	Laboratory Value
Hematology	
Absolute Neutrophil Count	<1000/mm ³ ; <1.0 x10 ⁹ /L
Hemoglobin	<10.0 g/dL; <6.2 mmol/L; <100 g/L
Platelet count	<75,000/mm ³ ; <75.0x10 ⁹ /L
Lymphocytes	<500/mm ³ ; <0.5x10 ⁹ /L
Chemistry	
AST ^a	>3x ULN

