ALT ^a	>3x ULN
Total bilirubin ^b	>1.5x ULN

- Additional investigations, such as review of ethanol, recreational drug and dietary supplement consumption should be done; testing for acute hepatitis A, B or C infection and biliary tract imaging should be promptly discussed with sponsor medical monitor.
- Total bilirubin >1.5 x ULN; participants with a history of Gilbert's syndrome may have a direct bilirubin measured and would be eligible for this study provided the direct bilirubin is <ULN.

Pregnancy

If pregnancy is confirmed by serum beta human chorionic gonadotropin (β -hCG) testing at any time, then the sponsor clinician or sponsor medical monitor should be notified immediately.

Suicidality

Participants triggering criteria for suicidal ideation and behavior as described in [Section 8.2.5.1](#).

See the [SoA](#) for data to be collected at the time of intervention discontinuation and follow-up and for any further evaluations that need to be completed.

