8.2.5.1. Columbia Suicide Severity Rating Scale

The Columbia Suicide Severity Rating Scale (C-SSRS)¹¹ is a validated tool to evaluate suicidal ideation and behavior ([Appendix 9](#)). “Lifetime” version will be used at screening and baseline and the “since last visit” version will be used in all subsequent visits.

If at any visit, there are “YES” answers on items 4, 5 or on any behavioral question of the C-SSRS, a risk assessment should be done immediately by a qualified medical health practitioner for appropriate evaluation and treatment. If the participant cannot be seen by a mental health professional within 24 hours, then the participant should be sent to a local emergency room for psychiatric assessment. If these answers occurred after IP dosing (ie, post-Day 1), IP will be temporarily discontinued until further evaluation. This evaluation will help determine whether it is safe for the participant to continue to participate in the trial. Participants who answer “YES” on items 4, 5 or on any behavioral question of the C-SSRS on more than one occasion during a trial will be discontinued from the trial.

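### The protocol gives conflicting instructions on study treatment after suicidal ideation or behaviour arising post-Day 1 (SoA C-SSRS footnote, Sections 7.1 and 8.2.5.1), and Section 6.1.1 does not provide for the resulting hold

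*Protocol*

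**What the plan says.** Four places in the current protocol bear on this.

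- **Section 1.3, C-SSRS footnote.** The trigger and action read "Participants who have recent or active suicidal ideation or behaviors will be excluded from study entry or after Day 1", and such participants "would be discontinued from treatment and referred to a mental health professional". No C-SSRS item threshold is given, and there is no pause or resumption.
- **Section 8.2.5.1.** The trigger is a YES on item 4, item 5 or any behavioural question. After dosing has started, "IP will be temporarily discontinued until further evaluation". The section adds: "This evaluation will help determine whether it is safe for the participant to continue to participate in the trial". Participants with such answers "on more than one occasion during a trial will be discontinued from the trial".
- **Section 7.1.** The site informs the sponsor "if the below criteria for permanent discontinuation of the IP are triggered". The Suicidality entry in that list reads "Participants triggering criteria for suicidal ideation and behavior as described in" Section 8.2.5.1, and says no more.
- **Section 6.1.1.** A temporary hold "for up to a maximum of 7 consecutive days is allowed once from Day 1 to Day 113" where the investigator deems it necessary. The reasons listed are infections, gastrointestinal disorders and haematological abnormalities.

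**The concern.** The footnote and Section 8.2.5.1 describe the same situation and prescribe different things. One takes the participant off treatment. The other suspends treatment and leaves the outcome to an evaluation. Section 7.1, where an investigator would look for the stopping rule, sends the reader back to 8.2.5.1, whose first step is temporary. The section that governs holds does not mention this one.

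This is a participant-safety rule. Two sites acting in good faith could treat the same event differently, and each could be cited for deviating from the other text. The difference also decides who remains on treatment in the Extension, whose primary objective is safety and tolerability.

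**Working it through.** No arithmetic applies. The check is to take specific events and read off what each passage requires.

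| Event after Day 1 | SoA footnote | Section 8.2.5.1 | Section 7.1 |
|---|---|---|---|
| First YES on item 4, item 5 or a behavioural question | Off treatment, referred; no return described | IP paused; evaluation informs whether to continue | Listed under permanent discontinuation, but defers to 8.2.5.1 |
| YES on item 3 only | Meets the trigger on its face | Trigger not met; no action on IP stated | Defers to 8.2.5.1 |
| Second qualifying YES | Already off treatment since the first | Discontinued from the trial | Defers to 8.2.5.1 |

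**First row.** This is the direct conflict. Under the footnote, treatment ends. Under 8.2.5.1, it may resume.

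**Second row.** The triggers differ as well. Appendix 9 titles item 3 as active ideation with a method but without intent to act. That falls within the footnote's wording but below the threshold in 8.2.5.1.

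**Third row.** The consequences differ in kind. The footnote ends treatment, while 8.2.5.1 ends trial participation. Section 7.1 states that stopping the product is not the same as leaving the study.

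**Hold provision.** The SoA schedules the post-baseline C-SSRS at Week 16 (Day 113) and Week 40 (Day 281). A hold that starts at a Week 16 visit held on its target day begins on the last day of the period in 6.1.1, and any later hold falls outside it. Section 8.2.5.1 sets no maximum duration. So 6.1.1 neither lists the reason for this hold nor covers the period in which a scheduled assessment would mostly trigger it.

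**Primary endpoint.**
1. SAP Section 4.4 sets binary data after withdrawal of study drug to failure. Estimand E1 uses data as recorded under inadequate compliance. In principle, then, a stop and a pause could be coded differently.
2. The first scheduled post-baseline C-SSRS is at the same visit as the Week 16 PASI, and an SoA footnote asks for procedures to be done before dosing. A stop triggered at that visit would not normally precede the primary assessment.
3. An effect therefore needs an event found off schedule before Week 16, in a participant who would otherwise have reached PASI 90.

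**Extension.** A first positive C-SSRS at Week 16 falls at the point of entry. The footnote would end treatment there. Section 8.2.5.1 would allow it to continue if the evaluation permits.

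**The case against.** The strongest reply is that the SoA describes itself as an overview and refers to the assessments section for detail, so 8.2.5.1 governs. On that reading the footnote is shorthand: it does not say that discontinuation is permanent, and both texts take the participant off IP at once and send them for mental-health assessment. Its trigger wording also resembles exclusion criterion 5 in Section 5.2, which does carry item thresholds. Section 7.1 could be read as importing only the repeat-event rule from 8.2.5.1. At Week 16, Section 4.1 separately lets the investigator keep a participant out of the Extension on safety grounds.

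Part of this stands: the immediate protection is similar, and the open question is mainly whether treatment may resume. But the overview statement sets no order of precedence, and Section 8 makes adherence to requirements in the SoA essential and bars waivers. The footnote does not refer to criterion 5. Even with those thresholds read in, the conflict over the action remains. Section 7.1 does not say which occurrence it means. The investigator's judgement in 4.1 is a separate gate and does not settle which instruction applies.

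Three stronger readings might be inferred, and the documents do not support them:

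- *Section 8.2.5.1 stops participants solely on a repeat.* It does not say so. The evaluation after a first event can also end participation; a repeat makes that mandatory.
- *Section 6.1.1 forbids this hold.* It lists reasons and a limit, but does not bar a hold required by another section. It is silent, which is a gap and not a prohibition.
- *The conflict shifts the primary result by one participant per event.* The schedule largely rules this out, and a switch matters just for a would-be responder.

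**Conclusion.** The contradiction is real and lies in current protocol text. For a first qualifying event after Day 1, a site cannot follow both the SoA footnote and Section 8.2.5.1. Section 7.1 does not resolve this, and 6.1.1 does not accommodate the hold. The point should be corrected for participant safety and consistent conduct, including continuation into the Extension.

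It is not a threat to the primary analysis: the effect on Week 16 PASI 90 is likely negligible, and no numerical size is claimed. That judgement assumes that the post-baseline C-SSRS follows the SoA (Weeks 16 and 40) and that the Week 16 PASI is done before any resulting stop. Section 8.2.5.1 refers to use of the scale at all subsequent visits. If sites read that as every visit, events could be detected earlier and the assumption would weaken. Events surfacing through adverse-event monitoring or unplanned visits before Week 16 remain possible in either case.

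**What to change.** Reconcile the trigger and the action in the SoA C-SSRS footnote, Section 7.1 and Section 8.2.5.1, and state them in the same words in each place. The text should make clear:

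- which C-SSRS answers count;
- what happens to IP at a first event and at a repeat;
- whether treatment, trial participation or both end;
- which occurrence the entry in 7.1 refers to.

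Make 6.1.1 consistent with the result, including for the Extension. Which rule applies is a decision for the sponsor's clinicians, and none is proposed here.

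The cost is protocol wording, by amendment or clarification letter. The reconciliation itself requires no change to the sample size or the planned analysis.
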